7. PLANNED ANALYSIS

Safety analysis (refer to [Section 7.8](#)) will be presented in Sections 15.1 to 15.4 of the CTR and in Appendix 16.1.13.1.

The prior specified in the CTP, Section 7.1 will be used in all BLRM evaluations.

The format of the listings and tables will follow the BI standards (see BI-KMED-BDS-HTG-0045 [\(8\)](#)) with the exception of those generated for PK-calculations [\(6\)](#).

The individual values of all patients will be listed, sorted by treatment group, patient number, and visit.

The listings will be included in Appendix 16.2 of the CTR.

The data of the last screening attempt of re-screened patients will be considered. In case a value from the last screening attempt of re-screened patients is missing this value will be imputed with the previous screening value.

For end-of-text tables, the set of summary statistics for non-PK parameters is:

N	number non-missing observations
Mean	arithmetic mean
SD	standard deviation

Min	minimum
Median	median
Max	maximum

Tabulations of frequencies for categorical data will include all possible categories and will display the number of observations in a category, as well as the percentage (%) for each treatment group. Percentages will be rounded to one decimal place and will be based on all patients in the respective subject set whether they have non-missing values or not. The category 'missing' will be displayed only if there are actually missing values.

Units of variables should be given in the titles or column/row descriptors in square brackets (e.g. [mg]).

7.1 DEMOGRAPHIC AND OTHER BASELINE CHARACTERISTICS

Only descriptive statistics are planned for this section of the report, based on the TS.

The data will be summarized by treatment group and in total.

7.2 CONCOMITANT DISEASES AND MEDICATION

Only frequency tables are planned for this section of the report, based on the TS.

Summaries will be presented for concomitant therapies ongoing at baseline and separately for those newly onset after first drug intake. Use of non-drug therapies will also be summarized.

Concomitant diseases and non-drug therapies will be coded using the latest version of the coding system of the Medical Dictionary for Drug Regulatory Activities (MedDRA). Medications will be coded using the latest version of the World Health Organization Drug Dictionary (WHO-DD). The coding version number will be displayed as a footnote in the respective output.

The diagnoses and medications and non-drug therapies will be listed. Patients without any concomitant diagnoses or concomitant therapies should be marked with a “No” in the respective column.

The relevance of the concomitant therapies to the evaluation of PK, efficacy and safety data will be decided no later than at the RPM/DBLM.

7.3 TREATMENT COMPLIANCE

Section 4.3 of the CTP:

Compliance will be assured by administration of all trial medication in the study centre. This is performed by a qualified physician. In the MD part the unmasked injector with no other involvement in the trial will administer the trial medication.

It is not intended to list the compliance separately. Any deviations from complete intake will be addressed in the RPM/DBLM (see [Section 6.2](#)) and described in the CTR.

7.4 PRIMARY ENDPOINT(S)

7.4.1 Primary analysis of the primary endpoint(s)

SRD part:

Section 5.2.1 of the CTP:

A DLE is defined as the occurrence of any of the following events in the study eye within the evaluation period (7 days after drug administration):

- *Development of sterile endophthalmitis and/or sterile inflammation of the vitreous grade 3+ according to the NEI Grading of vitreous haze, and anterior chamber cells of 3+ according to standardization of Uveitis Nomenclature (SUN) working group (WG) grading scheme for anterior chamber cells (see Table 5.2.1: 1 below) and a duration of 5 or more days between day 1 and day 8*
- *Visual loss of more than 15 letters at any given time-point*
- 
- *Signs of vascular occlusion in a 1st (the main branch) or 2nd degree (the vessel after the first bifurcation of the main branch) retinal vessel, including peripheral retinal hemorrhages in the area supplied by the occluded vessel (hemorrhage of the macula would not be included as this is a symptom of the disease).*

Section 5.2.7.1.4 of the CTP:

All AEs meeting the criteria for a dose limiting event (DLE) as defined in Section 5.2.1 are defined as AESIs for this trial.

Descriptive statistics (number and percentage of patients with DLEs) will be provided by dose group and in total.

MD part:

Descriptive statistics (number and percentage of patients with drug-related AEs) will be provided, based on the TS.

7.5 SECONDARY ENDPOINT(S)

7.5.1 Key secondary endpoint(s)

This section is not applicable as no key secondary endpoint has been specified in the protocol.

7.5.2 (Other) Secondary endpoint(s)

Section 7.3.2 of the CTP:

The secondary endpoints (refer to Section 5.2.2) will be summarized by means of descriptive statistics (at least n, mean, standard deviation, median, minimum and maximum) for continuous variables or frequency tables for categorical variables.

Analyses regarding safety and efficacy will be performed on the TS.

The change from baseline in FAZ area (separately for the superficial vascular complex and full thickness retina) over time will be analysed via a restricted maximum likelihood (REML) based approach using a mixed model with repeated measurements (MMRM) .

The model will include the fixed, categorical effects of treatment at each visit and the fixed continuous effects of baseline at each visit. Visit will be treated as the repeated measure with an unstructured covariance structure used to model the within-patient measurements.

The statistical model will be as follows

$$y_{ijk} = \beta_j S_i + \tau_{jk} + e_{ij}$$

$$e_{ij} \sim N_z(\mathbf{0}, \Sigma) .$$

y_{ijk} = response variable (as change from baseline) for subject i at visit j receiving treatment k ,

S_i = the baseline measurement of subject i , $i=1,2,\dots$

β_j = coefficient of baseline effect at visit j

τ_{jk} = the effect of treatment k at visit j , $j=1,\dots,Z$ and $k = 1, \dots, Y$,

e_{ij} = the random error associated with the j^{th} visit of the i^{th} subject. Errors are independent between subjects.

Σ = an unstructured covariance matrix

The Kenward-Roger approximation will be used to estimate denominator degrees of freedom and adjust standard errors. Least-squares means per treatment and for the treatment difference will be provided by time point, and in addition corresponding two-sided 95% confidence intervals and p-values will be presented.

In the event of non-convergence, the following methods will be attempted (in order) to overcome it:

1. Add the 'singular=1e-10' option in the model statement – This raises the threshold at which columns are declared linearly dependent (from typically 1e-12).
2. Set 'maxiter=100' in the Proc Mixed statement – This increases the number of convergence iterations used from a default of 50.

3. Set 'scoring=4' to specify use of the Fisher scoring algorithm in the first 4 iterations.
4. Include the statement 'performance nothread' – this removes multi-threading from the calculations.
5. Should none of the previous methods work, the covariance matrix will be changed from unstructured to Toeplitz with heterogeneous variances (TOEPH). Should this also not converge, a standard Toeplitz matrix (TOEP) will be fitted. Finally, if convergence still does not occur, then an order-1 autoregressive matrix (AR(1)) will be fitted.

The analysis will be performed on the TS. The above analysis is to be repeated for the below endpoints:

- i. The change from baseline in Central Retinal thickness over time.
- ii. The change from baseline in BCVA over time.
- iii. The change from baseline in FAZ area 3mm scan size in full thickness retina over time.

The focus in the CTR will be on the manually graded 3mm scan size FAZ FTR parameters, as such the pre-existing manually corrected FAZ FTR parameters (not assessed by scan size) will be placed in Appendix 16.1.13.1 and will not be described in the CTR.

For all continuous longitudinal secondary endpoints, time profiles of mean (\pm SD) absolute values and mean (\pm SD) changes from baseline by treatment group as well as individual time profiles (absolute values and changes from baseline) per treatment group will be provided for the study eye / fellow eye in addition.

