4. CHANGES IN THE PLANNED ANALYSIS OF THE STUDY

All analyses as planned in the CTP will be performed and are described in more detail in this TSAP.

For a more accurate reflection of the data, the term 'combined vascular complex' (CVC) for FAZ-related parameters has been renamed as 'full thickness retina' (FTR). For the MD part, the main assessment for FAZ parameters in FTR was changed to a manual grading of the 3mm OCTA scans i.e., the MD part endpoints related to FAZ area in FTR mentioned in the CTP are considered to be based on manually graded data for 3mm scan size. If an OCTA measurement is done for a specific scan size, this will be indicated in the endpoint label. For other OCTA endpoints where a measurement was not performed for a specific scan size, it will be deemed that the measurement was made primarily based on a 6mm scan size and if this was not possible then otherwise taken from a 3mm scan size.

Sensitivity statistical analysis of the efficacy endpoints using LOCF will not be performed as the handling of missing data is taken into account within the MMRM approach

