5.2.2 Secondary endpoint(s)

Section 2.1.3 of the CTP:

SRD part:

- number of patients with drug related AEs at EOS
- number of patients with ocular AEs (eye disorders) at EOS

MD part:

- change from baseline of the size of the FAZ area in optical coherence tomography angiography (OCTA) in superficial vascular complex and full thickness retina at Visit 5.
- change from baseline of the size of the FAZ area in optical coherence tomography angiography (OCTA) in superficial vascular complex and full thickness retina at Visit 7.
- change from baseline of BCVA at Visit 3
- change from baseline of BCVA at Visit 4
- change from baseline of BCVA at Visit 5
- change from baseline of BCVA at Visit 6
- change from baseline of BCVA at Visit 7
- change from baseline of Central retinal thickness (SD-OCT) at Visit 3
- change from baseline of Central retinal thickness (SD-OCT) at Visit 4
- change from baseline of Central retinal thickness (SD-OCT) at Visit 5
- change from baseline of Central retinal thickness (SD-OCT) at Visit 6
- change from baseline of Central retinal thickness (SD-OCT) at Visit 7
- number of patients with ocular AEs (eye disorders) at EOS

Note that the above FAZ area in FTR is understood to be the FAZ area in FTR for the 3mm scan size, manually graded.

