7.5.3 Interim analysis

Section 7.4 of the CTP:

For this trial, a "Fast track" analysis of the MD part is planned at Visit 6 (Week 16). After all data of the above-mentioned time point are available, a snapshot of the database will be taken.

This snapshot will be used for performing the Fast track analysis.

For the fast track analysis, the change from baseline in FAZ area 3mm scan size in full thickness retina over time will be analysed using the MMRM described in [Section 7.5.2](#), with the restriction that only visits up to Visit 6 (Week 16) are included in the model.

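### Does leaving the second full-thickness FAZ reading out of the CTR text, and allowing two scan sizes for superficial FAZ, call for a change to SAP 7.5.2?

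*SAP*

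**What the plan says.** SAP 4 renames the combined vascular complex as full thickness retina and then states: "For the MD part, the main assessment for FAZ parameters in FTR was changed to a manual grading of the 3mm OCTA scans". SAP 5.2.2 repeats this in a note to the secondary endpoints, where FTR FAZ is to be understood as "FAZ area in FTR for the 3mm scan size, manually graded".

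SAP 7.5.2 sets out the model: "The change from baseline in FAZ area (separately for the superficial vascular complex and full thickness retina) over time will be analysed" by MMRM. It then lists endpoints for which the same model is repeated, and item iii is "The change from baseline in FAZ area 3mm scan size in full thickness retina over time". For each model, "corresponding two-sided 95% confidence intervals and p-values will be presented". The section closes by saying that the CTR will concentrate on the 3 mm manual grading, while the older "manually corrected FAZ FTR parameters (not assessed by scan size) will be placed in Appendix 16.1.13.1 and will not be described in the CTR".

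For the Fast track analysis, SAP 7.5.3 names one FAZ reading: "the change from baseline in FAZ area 3mm scan size in full thickness retina over time will be analysed using the MMRM".

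For OCTA endpoints with no stated scan size, SAP 4 gives a rule that falls back on the 3 mm scan: "it will be deemed that the measurement was made primarily based on a 6mm scan size and if this was not possible then otherwise taken". Superficial FAZ has no scan size in its label, so this rule covers it.

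**The concern.** There are two readings of the same quantity in the same eyes, and only one will be discussed in the report. The protocol endpoint names neither a scan size nor a grading method, and the SAP text available attaches no reason to the change of grading. FAZ area is also the measure behind the sample-size reasoning for the multiple-dosing part (Protocol 7.1 and 7.7). With 20 active and 10 sham patients, two imperfectly correlated readings can give visibly different treatment differences by chance. Someone who read only the CTR narrative would not learn whether the FAZ result depends on how the images were graded.

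A smaller worry concerns superficial FAZ. If a patient has a 6 mm scan at baseline and a 3 mm scan later, or the reverse, any systematic offset between the sizes enters the change from baseline. The visible part of SAP 7.5.2 has no check that the two scans match.

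**Working it through.** **What is reported, and where.** The passages fit together as follows.

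- SAP 4 declares the change of main reading, for the multiple-dosing part only.
- SAP 5.2.2 fixes a single FTR endpoint, the 3 mm manual grading.
- SAP 7.5.2 sends the older FTR parameters to Appendix 16.1.13.1. SAP 7.8 describes that appendix as part of the CTR, so the older reading is reported and only the narrative leaves it out.
- SAP 5.3 lists FTR FAZ, with no scan size, among single-dose endpoints to be described in the CTR. The point therefore concerns the multiple-dosing part alone.
- It is probable, but not explicit, that both readings are modelled. SAP 4 says a specific scan size is shown in the endpoint label, so the unlabelled FTR model and item iii look like two readings. The note in SAP 5.2.2 equates FTR FAZ with the 3 mm grading, which would make item iii a duplicate.

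**How far two readings could differ.** The plan gives no figure to reproduce, because the planning SD and likelihoods in Protocol 7.7 are redacted. The inputs below are therefore partly assumed.

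- Arm sizes: 20 and 10 (Protocol 7.7).
- True effect: 10% (Protocol 7.1) of 0.766 mm² (Protocol 7.7) = 0.0766 mm². That mean is for deep FAZ and only stands in for FTR.
- Assumed: SD of change 0.05, 0.10 or 0.20 mm²; correlation ρ of the two estimated differences 0.5 to 0.95; the same true effect on both readings.

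SE = SD × √(1/20 + 1/10) = 0.3873 × SD.

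95% limit of the gap between the two estimates = 1.96 × SE × √(2(1 − ρ)).

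Disagreement on whether the 95% CI excludes zero = 2 × [P(reading 1 not significant) − P(neither significant)], taken from a bivariate normal with mean 0.0766/SE.

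| SD (mm²) | SE | 0.0766/SE | Gap limit, ρ = 0.5 to 0.95 (mm²) | Disagreement at ρ = 0.5, 0.8, 0.9, 0.95 |
|---|---|---|---|---|
| 0.05 | 0.0194 | 3.96 | 0.038 to 0.012 | 3.8%, 2.6%, 1.9%, 1.4% |
| 0.10 | 0.0387 | 1.98 | 0.076 to 0.024 | 33.3%, 20.5%, 14.4%, 10.1% |
| 0.20 | 0.0775 | 0.99 | 0.152 to 0.048 | 20.1%, 12.8%, 9.1%, 6.4% |

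A simulation of 40,000 trials with a two-sample t test (28 df) at SD 0.10 gave 33.9%, 21.1%, 14.9% and 10.4%, in agreement. The middle row is close to the worst case for disagreement: the standardised effect of 1.98 sits almost on the 1.96 cut-off, where two estimates fall most easily on opposite sides. A correlation of 0.5 is also low for two readings of the same eyes at the same visits, although the documents give no value.

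**Superficial FAZ.** Assume that 20% of baseline/follow-up pairs are mismatched, equally in both arms and both directions, with an offset of 0.02 to 0.08 mm². The expected bias is then zero. The SD of change grows by √(SD² + 0.2 × offset²)/SD − 1:

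- SD 0.05: 1.6% to 23.0%
- SD 0.10: 0.4% to 6.2%
- SD 0.20: 0.1% to 1.6%

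Bias needs switching that differs by arm. With 20 percentage points more one-way switching in one arm, it is 0.20 × 0.02 = 0.004 to 0.20 × 0.08 = 0.016 mm², which is 5.2% to 20.9% of 0.0766. The documents give neither the switching rate nor the offset, and nothing in them suggests a difference by arm.

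**The case for a change.** The strongest case for a change is that it costs little. When a main measurement is replaced after the protocol, in a trial whose sponsor functions work open label, showing the old result beside the new one lets the reader judge robustness. If the older reading is indeed modelled, the work is already planned, and a few lines with the treatment difference and 95% CI at Weeks 12 and 22 would suffice. The numbers above show that the two results need not agree.

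Some of this stands. A supportive sentence in the CTR would be courteous to the reader, and SAP 7.5.2 would be clearer if it named the reading behind each FTR model and confined the sentence on omission to the multiple-dosing part. But the reader already has the older result in a CTR appendix, at a place announced in advance. The images are read by an independent reading centre (Protocol 5.1), and holding the scan size constant is a sensible aim. The SAP history table is not available, so nothing can be inferred about when or why the grading was changed. Disagreement about whether a CI excludes zero also weighs little here: Protocol 7.2 plans no hypothesis test, and Protocol 5.7 calls OCT-A exploratory.

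For superficial FAZ, a supporting analysis of same-size pairs could be added if the reading centre can supply scan size. It would select patients on which follow-up scans could be obtained, in a 20 v 10 comparison, so it could introduce a selection effect while guarding against a bias that is only conjectured. Parts of SAP 5.3 and all of SAP 7.6 are not visible and may already contain such a check.

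**Conclusion.** No change to the plan is needed. The FTR point is a choice about narrative emphasis for an exploratory secondary endpoint: one reading is fixed in the SAP, the switch is disclosed, and the other reading stays in the CTR appendix. Moving it into the text would alter no estimate and no decision. The overlap between the unlabelled FTR model, item iii and the note in SAP 5.2.2 is a labelling slip that analysts can settle when they title the outputs.

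The possible disagreement between readings runs from about 1% to 33% of trials. It rests wholly on an assumed SD and correlation, a deep-FAZ mean used for FTR, and the planned 20 v 10 patients, so it illustrates what could happen and does not estimate it. For superficial FAZ, mixed scan sizes add noise (0.1% to 23% on the SD over the assumed range, at most about 6% at SD 0.10) and no expected bias unless switching differs by arm. A restricted analysis would gain little and brings a selection problem of its own.

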7.5.3 Interim analysis

Section 7.4 of the CTP:

For this trial, a "Fast track" analysis of the MD part is planned at Visit 6 (Week 16). After all data of the above-mentioned time point are available, a snapshot of the database will be taken.

This snapshot will be used for performing the Fast track analysis.

For the fast track analysis, the change from baseline in FAZ area 3mm scan size in full thickness retina over time will be analysed using the MMRM described in [Section 7.5.2](#), with the restriction that only visits up to Visit 6 (Week 16) are included in the model.

7.7 EXTENT OF EXPOSURE

Descriptive statistics are planned for this section of the report based on the TS. The date and time of drug administration will be listed for each patient.

7.8 SAFETY ANALYSIS

All safety analyses will be performed on the TS.

If not stated otherwise, the safety results will be sorted by treatment group.

The safety data for treated patients who failed to complete the study (dropouts or withdrawals) will be reported as far as their data are available. All withdrawals will be documented and the reason for withdrawal recorded.

Per the European Union (EU) Regulation 536/2014 (Annex V, Point 4) ([14](#)), the following information will be included in Appendix 16.1.13.1 of CTR:

- number of subjects included by country
- number of subjects inside (member states) and outside the EU (third countries)
- frequency of serious drug-related AEs by treatment, primary system organ class and preferred term.

7.8.1 Adverse Events

AEs will be coded with the most recent version of MedDRA.

The analyses of AEs will be descriptive in nature and will be based on BI standards as presented in “Analysis and Presentation of Adverse Event Data from Clinical Trials – Display Template” [BI-KMED-BDS-HTG-0041] ([9](#)).

Unless otherwise specified, the analyses of AEs will be descriptive in nature. All analyses of AEs will be based on the number of subjects with AEs and NOT on the number of AEs.

For analysis multiple AE occurrence data on the eCRF will be collapsed into an AE provided that all of the following applies:

- All AE attributes are identical (lower level term (LLT), intensity, action taken, therapy required, seriousness, reason for seriousness, relationship, outcome, AE of special interest (AESI))
- The occurrences were time-overlapping or time-adjacent (time-adjacency of two occurrences is given if the second occurrence started within one hour after end of the first occurrence)

Section 5.2.7.1.4 of the CTP: *The following are considered as AESIs:*

- *Hepatic injury*
A hepatic injury is defined by the following alterations of hepatic laboratory parameters:
 - *An elevation of AST (aspartate transaminase) and/or ALT (alanine transaminase) ≥ 3 -fold ULN combined with an elevation of total bilirubin ≥ 2 -fold ULN measured in the same blood sample, or*
 - *Aminotransferase (ALT, and/or AST) elevations ≥ 10 fold ULN*

These lab findings constitute a hepatic injury alert and the patients showing these lab abnormalities need to be followed up according to the 'DILI checklist' provided in the eDC. In case of clinical symptoms of hepatic injury (icterus, unexplained encephalopathy, unexplained coagulopathy, right upper quadrant abdominal pain, etc.) without lab results (ALT, AST, total bilirubin) available, the Investigator should make sure that these parameters are analysed, if necessary in an unscheduled blood test. Should the results meet the criteria of hepatic injury alert, the procedures described in the DILI checklist should be followed. All AEs meeting the criteria for a dose limiting event (DLE) as defined in Section 5.2.1 are defined as AESIs for this trial.

The analysis of adverse events will be based on the concept of treatment emergent adverse events.

Section 5.2.7.1.4 of the CTP: *For BI 764524 the residual effect period (REP) after IVT administration is not known. Therefore, all AEs with an onset between start of treatment and the respective EOS visit will be assigned to the on-treatment period for evaluation.*

According to ICH E3 (11), AEs classified as 'other significant' needs to be reported and will include those non-serious and non-significant adverse events with

- (i) 'action taken = discontinuation' or 'action taken = reduced', or
- (ii) marked haematological and other lab abnormalities or lead to significant concomitant therapy as identified by the Clinical Monitor/Investigator at the RPM/DBLM at the latest.

An overall summary of AEs (including number of patients with any AE, DLEs, drug related AEs, ocular AEs, AESIs, serious AEs and drug related serious AEs) will be presented.

The frequency of patients with AEs will be summarized by treatment, primary system organ class (SOC) and preferred term (PT). Separate tables will be provided for patients with other significant AEs according to ICH E3 (11), for patients with serious AEs, for patients with drug-related AEs, for patients with drug related serious adverse events for patients with AESIs, for patients with ocular AEs, and for patients with ocular AEs in the study eye.

The SOC and PTs will be sorted by frequency (within SOC). The MedDRA version number will be displayed as a footnote in the respective output.

In addition, frequencies of patients with non-serious AEs that had an incidence of > 5% for at least one treatment will be summarised by treatment, primary SOC and PT.

For disclosure of adverse events on EudraCT additional information not included in a standard AE analysis will be performed. The following three entries will be created:

- Adverse Events per arm for disclosure on EudraCT
- Non-serious Adverse Events for disclosure on EudraCT
- Serious Adverse Events for disclosure on EudraCT

For all ocular adverse events, ocular symptoms will be listed in addition.

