### 3.2                      DISCUSSION OF TRIAL DESIGN, INCLUDING THE CHOICE OF CONTROL GROUP(S)

This trial is designed to confirm that the MFD can be used for further testing in phase IIb trials. The trial consists of separate SRD and MD parts. The SRD dose escalation part is included and was designed with the goal to minimize the number of patients exposed to sub-therapeutic doses while on the other hand preserving safety and rapid dose finding. This part of the trial will be done in patients with DMI because IVT injections in healthy volunteers would not be considered appropriate. Whilst the drug may not benefit the participant directly during the trial, DMI is a chronic and bilateral disease. Therefore, if this trial leads to the approval of a treatment for DMI, the participant's other eye as well as the eye treated in the study may benefit from the treatment in the future. The worse seeing eye of the participant will be treated. As mentioned previously, risks are low but if the eye under trial treatment comes to harm, the impact on the patient will be less as the participants' visual function is driven by the better seeing eye. Dose escalation and cohort size will be decided by the SMC, guided by a BLRM with overdose control. An EWOC design will increase the chance of treating patients at efficacious doses while reducing the risk of overdosing. The use of BLRM for Phase I studies has also been advocated by the European Medicines Agency (EMA)

guideline on small populations [[R07-4856](#)] and by the Food and Drug Administration (FDA) [[R13-4881](#)].

One MD cohort (3 injections in 4-weekly intervals) will be included after the SRD part. Patients will be randomized either to active treatment group or to sham control group (ratio 2:1).

This part of the trial will generate additional safety data after multiple dosing and allow for exploration of the time course and durability of treatment effects. These data will further support the definition of the injection frequency and intervals in later studies.

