## 5. ASSESSMENTS

### 5.1 ASSESSMENT OF EFFICACY

For the endpoints, baseline is defined as the value at Visit 2; if not measured at Visit 2 then baseline is the value at Visit 1. All ophthalmologic examinations will be performed on both eyes, as described below.

Centrally collected ophthalmological data (color fundus photography, SD-OCT, OCT-A) will be transferred from the Central Reading Center (CRC) to the sponsor's database. The local measurement data (BCVA, Slit lamp, IOP, LLBCVA) will be transferred to the appropriate eCRFs and will remain at the study sites as source documents.

If clinically significant worsening is observed in the assessments of efficacy during the study, it will be reported as AE in the eCRF (please also refer to Section [5.2.7](#)).

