## 5.2 ASSESSMENT OF SAFETY

### 5.2.1 Dose limiting event

A DLE is defined as the occurrence of any of the following events in the study eye within the evaluation period (7 days after drug administration):

- Development of sterile endophthalmitis and/or sterile inflammation of the vitreous of grade 3+ according to the NEI Grading of vitreous haze, and anterior chamber cells of 3+ according to the Standardization of Uveitis Nomenclature (SUN) working group (WG) grading scheme (see Table 5.2.1: 1 below) and a duration of 5 or more days between day 1 and day 8
- Visual loss of more than 15 letters at any given time-point
- Persistent IOP over 30 mmHg for 3 days
- Signs of vascular occlusion in a 1st (the main branch) or 2nd degree (the vessel after the first bifurcation of the main branch) retinal vessel, including peripheral retinal hemorrhages in the area supplied by the occluded vessel (hemorrhage of the macula would not be included as this is a symptom of the disease).

Table 5.2.1: 1 The SUN Working Group Grading Scheme for Anterior Chamber Cells ([R18-1136](#))

Grade	Cells in Field 
0	<0
0.5+	1-5
1+	6-15
2+	16-25
3+	26-50
4+	>50

 Field size is a 1 mm by 1 mm slit beam.

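### The rule for collapsing AE records in SAP 7.8.1 does not list the affected eye, so the table of study-eye ocular AEs can lose an event or a patient

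*SAP*

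**What the plan says.** SAP 7.8.1 (Adverse Events) sets two conditions for merging several eCRF occurrences into one AE, and both must hold. The first reads "All AE attributes are identical (lower level term (LLT), intensity, action taken, therapy required, seriousness, reason for seriousness, relationship, outcome", and the list closes with AESI status. That makes nine attributes, with no wording to suggest they are only examples. The second is "The occurrences were time-overlapping or time-adjacent", where adjacent means that the later occurrence starts no more than one hour after the earlier one ends.

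The same section fixes the counting unit: "All analyses of AEs will be based on the number of subjects with AEs and NOT on the number of AEs". It then plans separate tables, among them "for patients with ocular AEs, and for patients with ocular AEs in the study eye".

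The secondary endpoint in SAP 5.2.2 is "number of patients with ocular AEs (eye disorders) at EOS", with no restriction by eye. The DLE definition in Protocol 5.2.1 is restricted: "A DLE is defined as the occurrence of any of the following events in the study eye". Protocol 5.1 says "All ophthalmologic examinations will be performed on both eyes, as described below", and Protocol 3.2 says "DMI is a chronic and bilateral disease".

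**The concern.** Which eye is affected decides whether an AE enters the study-eye table, but it is not among the attributes that keep two records apart. A merging rule should include every variable that a later table selects on. Otherwise the merge can remove the information that the table needs.

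Fellow-eye AEs can arise here, because both eyes are examined and the disease is described as bilateral. In a first-in-human trial of an intravitreal drug, the study-eye table shows local tolerability in the injected eye. A study-eye event that was recorded but is missing from that table would understate local AEs. In arms this small, one patient visibly changes a percentage.

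**Working it through.** The plan gives no figure on this point, so there is none to reproduce. The check applies the rule exactly as listed to one patient.

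**Inputs**
- Matching attributes and timing condition: SAP 7.8.1.
- Tables to be produced and counting unit (patients): SAP 7.8.1.
- Planned MD arm sizes, 20 active and 10 sham: SAP 6.1. That section also reports 32 patients enrolled in the MD part but not their split by arm, so the planned sizes are used.
- Assumed for illustration: two records with the same LLT, one per eye, both running from Day 10 to Day 15 and both mild, non-serious, unrelated and not AESI, with the other attributes also equal.
- Not given in the documents: which eye value a merged record keeps. Both possibilities are tried, for both orders of entry.

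**Step 1: rule as listed.** All nine attributes match and the dates overlap, so the two records become one in every case.

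| Record entered first | Eye value kept | Records left | In all-ocular table | In study-eye table |
|---|---|---|---|---|
| Study eye | first | 1 | yes | yes |
| Study eye | last | 1 | yes | **no** |
| Fellow eye | first | 1 | yes | **no** |
| Fellow eye | last | 1 | yes | yes |

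The event leaves the study-eye table in 2 of the 4 combinations, namely those where the fellow-eye value survives. These are enumerated cases and not a probability of one half.

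**Step 2: what does not merge.** If the study-eye event is a DLE, it is an AESI (Protocol 5.2.7.1.4), and a fellow-eye event cannot be a DLE. The AESI attribute then differs, two records remain and nothing is lost. The same holds if the study-eye event is rated drug-related and the fellow-eye event is not.

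**Step 3: effect on the other counts.** Merged records share the same relationship rating, so a patient with a drug-related AE stays counted as such. The merged record is still ocular, so the number of patients with any ocular AE is unchanged.

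**Step 4: size of one lost patient.** The patient drops out of the study-eye total only if there is no other study-eye AE. Otherwise only the preferred-term row changes. One patient is 100/20 = 5.0 percentage points in the active arm and 100/10 = 10.0 points in the sham arm.

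**Step 5: rule with eye as a tenth attribute.** The two records stay separate, and the patient is in the study-eye table in all four combinations.

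**The case against.** The strongest reply is that the condition speaks of all attributes. If the eye is recorded for each AE, as the study-eye table implies, it could be covered already. This reading is possible, but the parenthesis names the attributes one by one and a programmer would code that list. SAP 7.8.1 bases the AE analysis on a sponsor display standard, and SAP 6.1 refers to a technical dataset plan. Either may handle laterality, but neither is among the documents and the SAP does not point to them for it. If the program already uses the eye, the SAP text should say so.

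A second reply is that the loss needs several things at once: separate entries for each eye, agreement on all nine attributes, overlap or adjacency in time, and a merged record that keeps the fellow-eye value. A single both-eyes entry avoids it. Relationship and AESI keep many important events apart. Therapy required may do so too, since Protocol 4.2.2.1 treats the two eyes differently. Pre-existing findings are baseline conditions (Protocol 5.2.7.1.1), so bilateral disease does not by itself make matching on-treatment AEs common. All of this stands and limits the point to a possible loss. SAP section 7 also plans listings of individual values, which may let a careful reader find the event.

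Three stronger inferences are not supported:
- A reader might attach a probability to the loss. The documents give no rate of matching bilateral AEs and no rule for the eye value kept.
- A reader might take the study-eye table to be the only safety display specific to the treated eye. DLE counts are study-eye specific by definition.
- A reader might say that the two ocular tables would contradict each other. Study-eye AEs are a subset of ocular AEs, so a smaller count in that table is no contradiction.

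**Conclusion.** The gap is real and narrow. As listed, the collapsing rule can merge a study-eye record with a fellow-eye record, and the study-eye ocular AE table can then lose a preferred term. It loses the patient if that was the only study-eye AE: 5 points of 20 active or 10 points of 10 sham patients, at the planned sizes. This rests on reading the parenthesis as the full list and on the merged record keeping the fellow-eye value. The documents neither confirm nor exclude the second condition.

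A reader might infer that the main safety results are at risk. They are not: the primary endpoints (DLEs in the SRD part, drug-related AEs in the MD part) and the secondary count of patients with ocular AEs come out the same whether or not the records merge. What is exposed is one descriptive table, but it concerns the injected eye, and the correction is nearly free.

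**What to change.** In SAP 7.8.1, add affected eye (study / fellow / both / not applicable) to the attributes that must be identical before occurrences are collapsed, so that records for different eyes are never merged. This costs one phrase in the SAP and one extra key in the collapsing program. It needs no new data and changes no endpoint. If the program already separates the eyes, only the text needs to change.
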